### **9.8 Early Termination of the Study**

If the Sponsor or an Investigator believes it would be unsafe to continue the study, or for any reason at the Sponsor's request, the study may be terminated at that site or the entire study terminated after discussion with the other parties.

The Sponsor will provide a written statement to the IRB and the relevant regulatory authority with the reasons for termination of the study. This will be conducted within 15 days of the decision to terminate the study.

If the study is terminated, a close out monitoring visit will be performed and applicable procedures will be carried out to close the trial site(s).

PROTOCOL NUMBER: CCB-CRISIS-01  
PROTOCOL VERSION FINAL DATE: 10SEPT2020

Page 39 of 58

## 10 ADVERSE EVENT REPORTING

An adverse event is any untoward medical occurrence in a patient or clinical trial subject administered a medicinal product and which does not necessarily have a causal relationship with this treatment. An AE can therefore be any unfavorable and unintended sign (including an abnormal laboratory finding), symptom, or disease temporally associated with the use of the medicinal product, **whether or not considered related to the medicinal product.**

Events that occur prior to informed consent will be entered as medical history; AEs that occur after informed consent will be entered on the AE form.

Subjects will be questioned and observed for evidence of AEs, whether or not judged by the Investigator or designated person to be related to study drug. All AEs will be documented in the subject's medical record and CRF. For any pre-existing condition or abnormal laboratory finding that changes in severity after dosing, this change should be recorded as an AE. New abnormal laboratory findings that are clinically significant are considered AEs.

All adverse events will be collected from the time of informed consent through Day 15. After Day 15, collect/record only Serious Adverse Events (SAEs) or those judged by the Investigator or designated person to be related to study drug. AE details are to be documented including start and stop date and times, whether continuous or intermittent, severity, any intervention utilized to correct the event (e.g., medication, surgery, or other therapy), outcome and the relationship to the study drug.

AEs identified in the protocol as critical to the evaluation of safety must be reported to the Sponsor by the Investigator according to the reporting requirements within the time periods specified in the protocol.

AEs determined by the Investigator to be related to study drug must be followed until resolution or until they are considered stable or for at least 30 days after discontinuation of study drug.

Any serious adverse events (SAEs) experienced after 30 days post the last dose of study drug should only be reported to the sponsor if the investigator suspects a causal relationship to the study drug.

Abnormal laboratory values or test results occurring after study enrollment constitute AEs only if they induce clinical signs or symptoms, are considered clinically significant, or require therapy.

Death due to disease progression should not be reported as an SAE. Report death from disease progression on the appropriate electronic data capture form.

If a death occurs during the SAE reporting period, the cause of death such as pneumonia, ARDS, or respiratory failure, is considered as the AE and the death is considered its outcome. Death should be considered an outcome, not an event. The event or condition leading to death should be recorded and reported as a single medical concept on the AE eCRF. Generally, only one such event should be reported. "Fatal" will be recorded as the outcome of this respective event; death due to an outcome of an AE will not be recorded as separate event. If the primary cause of death is disease

PROTOCOL NUMBER: CCB-CRISIS-01  
PROTOCOL VERSION FINAL DATE: 10SEPT2020

Page 40 of 58

progression, the cause of death should be clearly identified as progression of the disease under study.

In cases of surgical or diagnostic procedures, the condition leading to the procedure is considered as the AE instead of the procedure itself. Each AE will be coded by the Sponsor from the verbatim text to a preferred term using a thesaurus based on the Medical Dictionary for Regulatory Activities (MedDRA). For example, record appendicitis, not appendectomy.

The following guidelines will be followed for the recording and reporting of adverse and serious adverse events.

1. The medical history section of the case report form will serve as the source document for baseline events.
  - a. Baseline events are any medical condition, symptom, or clinically significant lab abnormality present before the informed consent is signed.
    - i. If exact start date is unknown, month and year or year may be used as the start date of the baseline event.
2. Adverse events occurring after signing consent are to be recorded in the eCRF using the AE form.
3. Serious adverse events will be reported to the local IRB according to institutional policy.

The descriptions and grading scales found in the revised National Cancer Institute (NCI) Common Terminology *Criteria for Adverse Events (CTCAE) version 4.03* will be utilized for adverse event reporting. (<http://ctep.cancer.gov/reporting/ctc.html>).

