--	--

	
study drug-related AE or an SAE; the Day 29 mortality assessment is still to take place.
 
If the subject is unable or not permitted to return for planned study visits, the visit activities will be conducted by contacting the subject (phone or other digital media) except for the lab draw. The hematology/chemistry sample will be obtained via outpatient laboratory, if feasible and the results entered into the EDC and reviewed by the study team.
 
Study completion or the reason for study discontinuation will be recorded in the source document and the eCRF. A subject is considered completed the study if they have assessments through Day 15, whether conducted in the hospital or contacted via phone or other digital media.

Safety/ Tolerability
	
Safety/Tolerability
 
Adverse events will be collected from the time of informed consent through Day 15. After Day 15, collect/record only Serious Adverse Events (SAEs) or those judged by the Investigator or designated person to be related to study drug, including but not limited to potential hematologic toxicities. Post-randomization adverse events will be those with an onset after the date and time of randomization.
 
Subjects who develop Grade 3 or 4 toxicities are to be re-evaluated every 2 days, as feasible, until the toxicity returns to Grade <math>\leq 2</math> severity.

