## **6 TRIAL ENDPOINTS**

### **6.1 Primary Endpoint**

- Safety/tolerability measured by rates of post randomization adverse events and hematology/chemistry safety labs.

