#### **Day 29 (8 AM $\pm$ 3 days)**

- Determine survival status from EHR if available or contact the subject by phone call/digital media as acceptable to the institution.

If the subject is being discharged before Day 15, follow the procedures outlined in [Section 8.5](#).

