### **9.5.1 Unscheduled Visits**

Unscheduled visits and tests to assess AEs/SAEs are permitted as needed providing the AE related to study drug or SAE onset occurs within two (2) weeks after the final study dose.

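### The rule for recording worsening, the SAE reporting limit and the unscheduled-visit limit are all anchored to dosing, which the SOC arm never has, although the primary endpoint counts AEs from randomization in both arms

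*Protocol*

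**What the plan says.** The primary endpoint (Section 6.1) is "Safety/tolerability measured by rates of post randomization adverse events and hematology/chemistry safety labs". The Synopsis, under Safety/Tolerability, fixes the start of counting: "Post-randomization adverse events will be those with an onset after the date and time of randomization". Section 10 gives the general collection rule: "All adverse events will be collected from the time of informed consent through Day 15". None of these depends on study drug.

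Three other rules do depend on it:

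- **Worsening (Section 10):** "For any pre-existing condition or abnormal laboratory finding that changes in severity after dosing, this change should be recorded as an AE".
- **SAE reporting limit (Section 10):** any such event "experienced after 30 days post the last dose of study drug should only be reported to the sponsor if the investigator suspects a causal relationship".
- **Unscheduled visits (Section 9.5.1):** these are permitted "providing the AE related to study drug or SAE onset occurs within two (2) weeks after the final study dose".

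For the later period Section 10 adds: "After Day 15, collect/record only Serious Adverse Events (SAEs) or those judged by the Investigator or designated person to be related to study drug". In the Schedule of Events (Appendix A) the AE row is marked at Screening, Day 1, Days 1 to 7 and Day 15, and is blank in the last column. The Day 29 instruction in Section 9.5 is "Determine survival status from EHR if available or contact the subject by phone call/digital media as acceptable to the institution".

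**The concern.** Brequinar is given on Days 1 to 5 to about 16 subjects. About 8 subjects receive SOC alone and have no dose, so nothing in that arm can happen after dosing or within a set time of the last dose.

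The worsening rule matters in this population. Section 10 sends any condition, symptom or clinically significant laboratory abnormality present before consent to medical history. Inclusion criterion 10 requires at least one COVID-19 symptom, so every subject enters with something that could worsen. The one sentence that says explicitly when such worsening becomes an AE uses a trigger that exists in one arm only.

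The trial is open label, so site staff know which arm the trigger fits. If worsening is entered readily for brequinar and less readily for SOC, the arms differ in recorded AE rates without a true difference, to the disadvantage of brequinar. Those rates are the primary endpoint, and the DSMB compares the arms on safety after 6 and after 12 subjects complete Day 5 (Sections 10.9 and 10.9.1).

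**Working it through.** The protocol states no sample size, power or AE-rate calculation, so there is no figure of its own to reproduce. The check sets the rules side by side, does the day arithmetic and bounds the effect.

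**1. Which rules work in which arm**

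| Rule | Anchor | Brequinar | SOC |
|---|---|---|---|
| Post-randomization AE (Synopsis) | randomization | defined | defined |
| All-AE collection (Section 10) | consent to Day 15 | defined | defined |
| Abnormal laboratory value as AE: symptomatic, clinically significant or needing therapy (Section 10; see also 10.8) | enrollment | defined | defined |
| Worsening of a pre-existing condition or laboratory finding (Section 10) | dosing | defined | no anchor |
| SAE reporting limit (Section 10) | last dose + 30 days | defined | no anchor |
| Unscheduled visits (Section 9.5.1) | final dose + 2 weeks | defined | no anchor |
| Non-serious AEs after Day 15 (Section 10) | judged drug-related | defined | in practice none |

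**2. Day arithmetic, brequinar arm**

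- SAE limit: last dose on Day 5 gives 5 + 30 = Day 35. If only the Day 1 dose is taken, 1 + 30 = Day 31.
- Unscheduled visits: 5 + 14 = Day 19 (1 + 14 = Day 15 after a single dose).
- From the last scheduled AE entry to the SAE limit: 35 − 15 = 20 days, or 18 to 22 with the ±2-day window.
- From the Day 29 survival check to the SAE limit: 35 − 29 = 6 days, or 3 to 9 with the ±3-day window.
- For SOC neither limit can be computed.

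**3. Bound on the effect of one-sided recording**

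The documents give no rate of worsening, so this is an assumption shown over a range. Let a share s of subjects in each arm have, as their only AE, a worsening that is recorded in brequinar and not recorded in SOC. The arms then differ by s with no true difference. Expected subjects counted in brequinar = 16s. Expected subjects missed in SOC = 8s. The chance that at least one SOC subject is missed = 1 − (1 − s)^8.

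| s | Counted, of 16 | Missed, of 8 | Chance of at least one missed |
|---|---|---|---|
| 5% | 0.8 | 0.4 | 34% |
| 10% | 1.6 | 0.8 | 57% |
| 20% | 3.2 | 1.6 | 83% |
| 30% | 4.8 | 2.4 | 94% |

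Each row is the ceiling for its s, because it supposes that no such SOC event is entered. Any recording under the general rules lowers it.

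**The case against.** The worsening sentence includes events; it does not say that worsening in an undosed subject is not an AE. Section 10 also requires AEs after consent to go on the AE form in both arms, and Section 9.5 has progress notes reviewed daily until discharge for everyone. A careful site would enter SOC worsening under these rules. That stands: a reader might infer that worsening is recorded in the brequinar arm only, and the text does not support this. For laboratory findings the inference is wrong where the change is clinically significant, since the enrollment-anchored rule already covers it.

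A reader might also infer that the primary AE rates cover different periods in the two arms. Through Day 15 they do not: counting starts at randomization and all AEs are collected in both. SAEs after Day 15 are likewise collected in both.

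Nor do the 30-day and two-week limits define the AE rate. One governs reporting to the sponsor, the other when extra visits are allowed. The absence of AE contact after Day 15 is not complete either: Section 10.8 gives subjects discharged before Day 7 a Day 29 contact, and phone visits ask about bleeding signs.

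Finally, this is a phase 1a trial of about 24 subjects with descriptive analyses, and an analysis window can be set in the SAP. That is fair for the window. It does not help with worsening in SOC that was never entered on the AE form.

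**Conclusion.** The point holds in a limited form. Three rules refer to dosing and have no meaning for SOC, while the primary endpoint counts from randomization in both arms. The consequence is a risk of inconsistent, allocation-aware recording in SOC, mainly of non-laboratory worsening. Its size cannot be derived from the protocol. The table above is conditional on the assumed s and on complete non-recording in SOC, and the protocol gives no basis for assuming that most AEs are worsening of entry conditions.

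After Day 15 the plan asks for SAEs in both arms without a scheduled general AE query, for about 20 days up to the brequinar reporting limit when all five doses are taken. Non-serious AEs in that period are kept only if drug-related, which in practice means brequinar only. An all-AE table without an end day would therefore mix unlike event sets.

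This is a modest wording correction that does not put the trial's conduct in doubt. It is best made early because the SAP cannot restore unrecorded events.

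**What to change.** 1. In Section 10, replace *after dosing* by *after randomization* in the worsening sentence, for both arms.
2. Express the SAE reporting limit (Section 10) and the unscheduled-visit limit (Section 9.5.1) in Study Days that apply to both arms, and reconcile the two. The choice of days is the sponsor's.
3. Restrict the comparative all-AE table to onset from randomization through Day 15. List later drug-related reports separately.
4. Add an AE/SAE question to the Day 29 contact, with a mark in the AE row of Appendix A.

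The cost is a few sentences, one mark in the schedule and one extra question at Day 29. Where survival would otherwise be read from the EHR, it also means a call to the subject.

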#### 8.4.2 Study-Level Stopping Criteria

Following assessment by the Data Safety Monitoring Board (DSMB, see [Section 10.9](#)), the study is to be stopped as shown below:

- If  $\geq 4$  subjects on the brequinar treatment arm develop the same Grade 3 or 4 adverse event or symptomatic laboratory abnormality
- If  $\geq 8$  subjects on the brequinar treatment arm develop any Grade 3 or 4 adverse event or symptomatic laboratory abnormality.

### 8.5 Hospital Discharge Prior to Study Day 15

Subjects discharged from the hospital prior to the Day 15 visit are to return to a research facility when feasible for the remaining study visits. All scheduled study assessments are to be completed at these visits when conducted at a research facility.

PROTOCOL NUMBER: CCB-CRISIS-01  
PROTOCOL VERSION FINAL DATE: 10SEPT2020

Page 30 of 58

For subjects in the brequinar treatment group discharged from the hospital prior to Day 5, the subject is to take home the remaining doses of brequinar for daily self-administration. All subjects (brequinar and SOC) should have the scheduled assessments, e.g. lab samples and the nasopharyngeal swab, on the day of discharge and enter these results on the appropriate EDC page. Following discharge, subjects are to return to the research or out-patient lab collection facility for the remaining study visits, if feasible. Out-patient lab results are to be entered into the EDC and reviewed by a member of the study team. It is important that every effort be made to have subjects return at least on Days 7 and 15, if feasible. Subjects in the brequinar group are to record brequinar dosing on the medication diary provided by the study team. The study team will arrange for the subject to return any unused study medication to the research facility.

For all subjects, if discharge occurs on Days 10, 11, or 12, ensure a hematology/chemistry sample has been obtained on the day of discharge and record these results on the appropriate EDC page. Following discharge, the subject is to return to the research or out-patient lab collection facility for the Day 15 visit, if feasible. Out-patient lab results are to be entered into the EDC and reviewed by a member of the study team.

If discharge occurs on Days 13, 14 or 15, complete the Day 15 Final Visit activities prior to discharge. No further visits are required unless follow up is needed for a study drug-related AE or an SAE; the Day 29 mortality assessment is still to take place.

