#### **10.5 Serious Adverse Event (SAE) Reporting**

The regulatory definition of an SAE is any untoward medical occurrence or effect that at any dose:

- results in death;
- is life threatening (at the time of the event);
- requires in-patient hospitalization or prolongation of existing hospitalization;
- results in persistent or significant disability / incapacity, or
- is a congenital anomaly / birth defect;
- all other events that are considered medically serious by the Investigator.

**Disability** is defined as a substantial disruption of a person’s ability to conduct normal life functions.

**A life-threatening adverse event** is one that places the patient/subject, in the view of the Investigator, at immediate risk of death from the event as it occurred. It does not include an event that, had it occurred in a more severe form, might have caused death.

**An unexpected adverse event** is any adverse drug event, the nature or severity of which is not consistent with the applicable product information (e.g. IB for an unauthorized investigational product or summary of product characteristics for an authorized product).

PROTOCOL NUMBER: CCB-CRISIS-01  
PROTOCOL VERSION FINAL DATE: 10SEPT2020

Page 42 of 58

Enter only one event as the reason for the SAE on the SAE form. Other non-serious events which did not directly result in the SAE should be detailed in the description section on the SAE form and listed separately as AEs if necessary. For fatal SAEs, report the cause of death as an SAE with a fatal outcome rather than reporting death as the SAE term.

Note that hospitalizations for the following reasons should not be reported as SAEs:

- Routine treatment or monitoring of the studied indication, not associated with any deterioration in condition;
- Elective or pre-planned treatment for a pre-existing condition that is unrelated to the indication under study and has not worsened since signing the informed consent;
- Social reasons and respite care in the absence of any deterioration in the subject's general condition;
- Note that treatment on an emergency outpatient basis that does not result in hospital admission and involves an event not fulfilling any of the definitions of an SAE given above is not an SAE.

Death due to disease progression is considered to be an Expected event in patients with severe SARS-CoV-2 infection and does not require reporting on an expedited basis.

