#### **10.9.1 DSMB Safety Review Schedule**

The DSMB is to review adverse events and safety laboratory assessments after the first six subjects complete Day 5 of treatment, and again after the first 12 subjects complete Day 5 of treatment.

PROTOCOL NUMBER: CCB-CRISIS-01  
PROTOCOL VERSION FINAL DATE: 10SEPT2020

Page 46 of 58

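### The protocol gives incompatible recording rules for a COVID-19 progression death, and its study-level stopping limits do not say whether a fatal event counts

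*Protocol*

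**What the plan says.** References are to the protocol version of 10 September 2020, the latest in the file.

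**Recording of deaths**

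- Section 10 states: "Death due to disease progression should not be reported as an SAE". It goes on: "Report death from disease progression on the appropriate electronic data capture form". The form is not named.
- The next paragraph of Section 10 deals with deaths that fall while SAEs are still being collected, and says: "the cause of death such as pneumonia, ARDS, or respiratory failure, is considered as the AE and the death is considered its outcome". It places that event on the AE form, generally asks for one event per death, and ends by asking that a death caused mainly by progression be identified as such.
- Section 10.5 includes in its SAE definition, without exception, any occurrence that "results in death", and instructs: "For fatal SAEs, report the cause of death as an SAE with a fatal outcome rather than reporting death as the SAE term". Its block in capitals requires every SAE within 24 hours. It also calls a progression death in severe infection expected, and says it "does not require reporting on an expedited basis".
- Section 10 collects all AEs to Day 15. After that it collects only SAEs and events judged related to study drug.

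**Stopping and monitoring**

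- Section 8.4.2, like the synopsis, stops the study if 4 or more "subjects on the brequinar treatment arm develop the same Grade 3 or 4 adverse event or symptomatic laboratory abnormality". The second limit is 8 or more such subjects with any event of that kind. Neither limit mentions a fatal outcome, and no death-based limit appears elsewhere.
- Section 10.9.1: "The DSMB is to review adverse events and safety laboratory assessments after the first six subjects complete Day 5 of treatment". A second review of the same kind follows at 12 subjects. Deaths are not named as an input.

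**The concern.** In a trial of hospitalised COVID-19 patients, pneumonia, ARDS and respiratory failure are the usual forms that disease progression takes; Section 3.2 itself lists ARDS as a complication of severe cases. The examples in the second paragraph are therefore the same deaths that the first paragraph removes from SAE reporting. Two sites could follow the text faithfully and record the same death differently.

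This matters for three reasons. First, the primary endpoint (Section 6.1) is built on AE rates, and Section 11.2 also summarises SAEs. Second, the trial is open-label (Section 8.8.3), so whoever decides between progression and adverse event knows the arm. Third, Section 8.2.1 lists leukopenia and infection among the commonly observed adverse events of brequinar. A worse course of infection is then at least a conceivable drug harm, and it would fall in the exempted category.

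The stopping limits raise a related question. If an event recorded only as fatal lies outside the Grade 3 or 4 wording, the most serious outcome adds nothing to the count.

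**Working it through.** The protocol gives no operating characteristics for the stopping limits and no expected death rate, so there is no figure to reproduce. The check is a comparison of the text, followed by a count.

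**Step 1. One death, followed through each instruction.** Take a subject who dies of ARDS, attributed to COVID-19 and judged unrelated to study drug.

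| Text followed | Result |
|---|---|
| Section 10, progression sentence | Not an SAE; separate data form |
| Section 10, next paragraph | AE (ARDS) with fatal outcome, on the AE form |
| Section 10.5, definition and 24-hour block | SAE, due within 24 hours |
| Section 10.5, closing sentence | Expected; exempt from expedited reporting only |

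Rows 3 and 4 could coexist if the exemption concerns only onward expedited reporting, though the text does not say so. Row 1 cannot be reconciled with row 3. Rows 1 and 2 can both be followed only by holding a fatal AE that is not serious, which the Section 10.5 definition rules out.

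**Step 2. The same death after Day 15.** On Days 16 to 29 an event is collected only if it is an SAE or drug-related. Under row 1 it is not an SAE, and by assumption it is not drug-related. It therefore need not enter the AE data. It would still appear on the separate form and in the Day 29 survival status.

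**Step 3. The stopping count.** Inputs: approximately 24 subjects allocated 1:2 (Section 7.1), so 24 × 2/3 = 16 on brequinar and 24 × 1/3 = 8 on standard of care. The limits of 4 and 8 are 4/16 = 25% and 8/16 = 50% of the brequinar arm.

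Let k be the brequinar subjects with a recorded Grade 3 or 4 event, and f the further subjects whose only severe event is recorded as fatal. The literal count is k; the count including fatal events is k + f. Take k = 7, all with different events, and f = 3.

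- Same-event limit: the largest literal count for one event is 1, below 4.
- Any-event limit: the literal count is 7, below 8.
- Including fatal events: 7 + 3 = 10, which is at least 8.

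So 10 of 16 subjects (62.5%) have a severe or fatal event and neither limit is literally met. With k = 7, f = 1 is already enough for the two readings to differ (7 against 8). The same holds for one event term with 3 non-fatal cases and 1 fatal-only case (3 against 4).

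The count does not depend on how the adopted toxicity scale labels a fatal event. The protocol does not spell that out, and the limits name no fatal outcome.

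**The case against.** A reader might infer that deaths fall outside every safety trigger. The documents do not support that. Day 29 mortality is a secondary endpoint in both arms (Section 6.2). The DSMB compares the arms for safety and may advise stopping (Section 10.9). The sponsor or an investigator may end the study as unsafe with no grade condition (Section 9.8). Section 10.6 has investigators supply further information on reported deaths when asked. Deaths not attributed to progression remain SAEs.

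A reader might also infer that no death among the 16 brequinar subjects could ever count toward stopping. That too goes too far. Section 10 treats death as an outcome and records severity separately, so a fatal event may carry a Grade 3 or 4 severity. A subject with a recorded Grade 3 or 4 event who later dies is already counted. What remains is the subject with only a fatal record. The request for generally one event per death means that an earlier Grade 3 or 4 entry is not assured.

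The best defence of Section 10 is its closing sentence on identifying progression as the cause. It allows a reading in which the event goes on the AE form as fatal and labelled progression, but is not sent as an SAE. On that reading, deaths to Day 15 are in the AE data and reach the DSMB. This narrows the problem, but the conflict with Section 10.5 and the gap after Day 15 remain.

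Two further points stand. Leukopenia and infection are not among the related events that Section 8.2.1 lists for the 39 subjects at or below 100 mg for five days, so the harm route is conceivable rather than expected. The DSMB charter is a separate document that is not shown and may already ask for deaths by arm.

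**Conclusion.** The point holds in two parts. First, Sections 10 and 10.5 give incompatible instructions for a death attributed to COVID-19 progression, and after Day 15 one of them lets an unrelated progression death stay out of the AE data. Second, Section 8.4.2 and the synopsis leave unstated whether an event recorded only as fatal counts; read literally, it does not.

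The consequence is that the AE and SAE data and the pre-specified limits depend on an open-label judgement of progression, and that the scheduled DSMB inputs do not name deaths. Deaths are not hidden from the trial.

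The size is best shown by the count above: 10 of 16 brequinar subjects affected with neither limit literally met, and a single fatal-only record able to decide the matter. This rests on the literal wording and on those subjects having no earlier recorded Grade 3 or 4 event. A probability of four or more deaths would not measure the defect: the protocol gives no mortality rate, four deaths need not share one event term, and the scheduled reviews are tied to completion of Day 5 rather than to Day 29.

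This is an error in a written rule, not detail that could be left to the statistical analysis plan.

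**What to change.** 1. Reconcile Sections 10 and 10.5, including the 24-hour block and the collection rule after Day 15, into one recording rule for all deaths in both arms through Day 29. Keep COVID-19 progression as a cause or attribution field, and confine any exemption to expedited reporting, as the closing sentence of Section 10.5 already does.
2. Have the sponsor and DSMB state in Section 8.4.2 and the synopsis whether fatal events count toward the existing limits. Which answer is right, and the limits themselves, are for them to decide; the text must say one thing.
3. Name deaths by arm among the scheduled review inputs in Section 10.9.1 and the DSMB row of the synopsis, consistent with the charter.

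The cost is wording in these sections and a few extra forms in a trial of about 24 subjects. No assessment or visit is added.
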